5.4 APPENDIX 4 DATA HANDLING CONVENTIONS

Analysis windows for time points

Unless stated otherwise, the following analysis windows ([Table 10](#), [Table 11](#), and [Table 12](#)) will decide how the post-baseline scheduled and/or unscheduled visits will be used in the by-visit analyses of efficacy, safety, biomarker and ADA variables.

A measurement (scheduled or unscheduled) will be used if it is available and measurement date is within the analysis window.

After applying these time windows, if multiple assessments are associated with the same time point, the closest from the targeted study day will be used. If the difference is a tie, the value after the targeted study day will be used. If multiple valid values exist within a same day, then the first value of the day will be selected.

If there is no measurement for a given parameter in an analysis window, data will be considered missing for the corresponding visit.

Table 10 - Analyses window definition for participants assigned to PK - Schedule A

Scheduled visit post baseline	Targeted study day	Analysis window in study days
Week 1 (Visit 3A)	8	2 to 46
Week 12 (Visit 4)	85	47 to 127
Week 24 (Visit 5 – EOT)	169	128 to 211
Week 36 (Visit 6 – EOS)	253	≥212

Study days are calculated considering Day 1 as the day of first administration of intervention.

Table 11 - Analyses window definition for participants assigned to PK - Schedule B

Scheduled visit post baseline	Targeted study day	Analysis window in study days
Week 2 (Visit 3B)	15	2 to 50
Week 12 (Visit 4)	85	51 to 127
Week 24 (Visit 5 – EOT)	169	128 to 211
Week 36 (Visit 6 – EOS)	253	≥212

Study days are calculated considering Day 1 as the day of first administration of intervention.

Table 12 - Analyses window definition for participants following the Schedule of Activities from initial version of the protocol dated of 30-Mar-2022

Scheduled visit post baseline	Targeted study day	Analysis window in study days
Week 1 (Visit 3)	8	2 to 11
Week 2 (Visit 4)	15	12 to 22
Week 4 (Visit 5)	29	23 to day 57
Week 12 (Visit 6)	85	58 to day 127
Week 24 (Visit 7 – EOT)	169	128 to 211
Week 36 (Visit 8 – EOS)	253	≥212

Study days are calculated considering Day 1 as the day of first administration of intervention.

Unscheduled visits

Unscheduled visit measurements of laboratory data, vital signs, biomarker and ADA will be used for computation of baseline, the last on-treatment value and analysis according to PCSAs. They will also be included in the by-visit summaries if they are re-allocated to scheduled visits.

5.5 APPENDIX 5 PCSA

CRITERIA for POTENTIALLY CLINICALLY SIGNIFICANT ABNORMALITIES For Studies in Children

Parameter	Age range	PCSA	Comments
Vital Signs			Ref.: Kidney Disease Outcomes Quality Initiatives (KDOQI) Guideline 13; 1996; The fourth report on the diagnosis, evaluation, and treatment of high blood pressure in children and adolescents, Pediatrics 2004; Bowman E & Fraser S Neonatal Handbook 2012; Mulberg AE et al. Pediatric Drug Development Concepts and applications. John Wiley & sons, Inc. 2009; Pediatric respiratory rates http://www.health.ny.gov/
SBP	Birth/0 to 27 days old (Neonates)	≤ 60 mmHg and decrease from baseline ≥ 20 mmHg ≥ 85 mmHg and increase from baseline ≥ 20 mmHg	Based on definition of Hypertension as average SBP or DBP $\geq 95^{\text{th}}$ percentile for gender, age, and height on ≥ 3 occasions
	28 days/1 month to 23 months old (Infants)	≤ 70 mmHg and decrease from baseline ≥ 20 mmHg ≥ 98 mmHg and increase from baseline ≥ 20 mmHg	
	24 months/2 years to <6 years old (Children)	≤ 70 mmHg and decrease from baseline ≥ 20 mmHg ≥ 101 mmHg and increase from baseline ≥ 20 mmHg	
	6 to <12 years old (Children)	≤ 80 mmHg and decrease from baseline ≥ 20 mmHg ≥ 108 mmHg and increase from baseline ≥ 20 mmHg	
	12 to 16/18 years old (Adolescents)	≤ 90 mmHg and decrease from baseline ≥ 20 mmHg ≥ 119 mmHg and increase from baseline ≥ 20 mmHg	
DBP	Birth/0 to 27 days old (Neonates)	≤ 34 mmHg and decrease from baseline ≥ 10 mmHg ≥ 50 mmHg and increase from baseline ≥ 10 mmHg	
	28 days/1 month to 23 months old (Infants)	≤ 34 mmHg and decrease from baseline ≥ 10 mmHg ≥ 54 mmHg and increase from baseline ≥ 10 mmHg	
	24 months/2 years to <6 years old (Children)	≤ 34 mmHg and decrease from baseline ≥ 10 mmHg ≥ 59 mmHg and increase from baseline ≥ 10 mmHg	
	6 to <12 years old (Children)	≤ 48 mmHg and decrease from baseline ≥ 10 mmHg ≥ 72 mmHg and increase from baseline ≥ 10 mmHg	
	12 to 16/18 years old (Adolescents)	≤ 54 mmHg and decrease from baseline ≥ 10 mmHg ≥ 78 mmHg and increase from baseline ≥ 10 mmHg	
Orthostatic hypotension	All age ranges	SBP : St — Su ≤ -20 mmHg DBP : St — Su ≤ -10 mmHg	
Temperature	All age ranges	Rectal, ear or temporal artery: $\geq 100.4^{\circ}\text{F}/38.0^{\circ}\text{C}$ Oral or pacifier: $\geq 9.5^{\circ}\text{F}/37.5^{\circ}\text{C}$ Axillary or skin infrared: $\geq 99^{\circ}\text{F}/37.2^{\circ}\text{C}$	Ear temperature not accurate below 6 months of age

CRITERIA for POTENTIALLY CLINICALLY SIGNIFICANT ABNORMALITIES For Studies in Children			
Parameter	Age range	PCSA	Comments
Respiratory rate	Birth/0 to 27 days old (Neonates)	<30 per minutes >60 per minutes	Based on normal range
	28 days/1 month to 23 months old (Infants)	<24 per minutes >40 per minutes	
	24 months/2 years to <6 years old (Children)	<22 per minutes >34 per minutes	
	6 to <12 years old (Children)	<18 per minutes >30 per minutes	
	12 to 16/18 years old (Adolescents)	<12 per minutes >20 per minutes	
	All age ranges	≤95%	
Weight	All ranges	≥% weight loss from baseline	Based on identification of trends in the child's growth with a series of visits WHO Multicentre Reference Study Group, 2006; Center for Disease Control. Growth chart 2007
Clinical Chemistry			
ALT/SGPT	All age ranges	≥3 ULN	Ref Molleston JP et al. JPGN 2011;
		By distribution analysis:	Moritz et al., Pediatrics 1999; Moritz et al., Pediatr Nephrol 2005 ; Sedlacek et al., Seminars in Dialysis 2006) Gong G et al. Clinical Biochemistry 2009;
		≥3 ULN	Masilamani et al. Arch Dis Children 2012; Mulberg AE et al. Pediatric Drug Development Concepts and applications. John Wiley & sons, Inc. 2009
		≥5 ULN	
		≥10 ULN	
		≥20 ULN	
AST/SGOT	All age ranges	≥3 ULN	Based on normal ranges: 6 to 50 U/L (0-5 days), 5 to 45 U/L (1-19 years)
		By distribution analysis:	
		≥3 ULN	140 U/L (0-5 days), 15 to 55 U/L (1-9 years), 5 to 45 U/L (10-19 years)
		≥5 ULN	
		≥10 ULN	
		≥20 ULN	
Alkaline Phosphatase	All age ranges	≥1.5 ULN	Based on normal ranges: 145 to 420 U/L (1-9 years), 130 to 560 U/L (10-11 years), 200 to 495 U/L (Boys 12-13 years), 105 to 420 U/L (Girls 12-13 years), 130 to 525 U/L (Boys 14-15 years), 70 to 130 U/L (Girls 14-15 years), 65 to 260 U/L (Boys 16-19 years), 50 to 130 U/L (Girls 16-19 years)

**CRITERIA for POTENTIALLY CLINICALLY SIGNIFICANT ABNORMALITIES
For Studies in Children**

Parameter	Age range	PCSA	Comments
Total Bilirubin	All age ranges	$\geq 1.3 \text{ ULN}$	$CF = mg \times 1.7 = \mu\text{mol}$ Based on normal ranges: <6 mg/dL (Term 0-1 day), <8 mg/dL (Term 1-2 days), <12 mg/dL (Term 3-5 days), <1 mg/dL (Term >5 days)
Conjugated Bilirubin	All age ranges	$>35\% \text{ total bilirubin and TBILI} \geq 1.3 \text{ ULN}$	$CF = mg \times 1.7 = \mu\text{mol}$ Based on normal range: 0 to 0.4 mg/dL
ALT and Total Bilirubin	All age ranges	$ALT \geq 3 \text{ ULN}$ and $\text{Total Bilirubin} \geq 2 \text{ ULN}$	
CPK	All age ranges	$\geq 3 \text{ ULN}$	
Creatinine	Birth/0 to <6 years old (Neonates, Infants, Children)	$>53 \mu\text{mol/L}$ or 0.6 mg/dL	$CF = mg \times 8.8 = \mu\text{mol}$ Based on normal ranges: $\leq 0.6 \text{ mg/dL}$ (0-1 year), 0.5 to 1.5 mg/dL (1 to 16/18 years)
	6 years to <12 years old (Children)	$>90 \mu\text{mol/L}$ or 1.1 mg/dL	
	12 years to 16/18 years old (Adolescents)	$>132 \mu\text{mol/L}$ or 1.5 mg/dL	
Creatinine Clearance	All age ranges	50% of normal $<60 \text{ mL/min/1.73m}^2$ (After 1 year old)	Based on GFR Bedside Schwartz Formula Based on normal ranges: 20 to 50 (<8 days), 25 to 80 (8 days to 1 month), 30 to 90 (1-6 months), 40 to 115 (6-12 months), 60 to 190 (12-23 months), 90 to 165 (2-12 years), 80-120 (After 12 years)
Uric Acid	All age ranges	$\leq 2.0 \text{ mg/dL}$ or $119 \mu\text{mol/L}$ $\geq 8.0 \text{ mg/dL}$ or $476 \mu\text{mol/L}$	$CF = mg \times 5.95 = \mu\text{mol}$ Based on normal ranges: 2.4 to 6.4 mg/dL
Blood Urea Nitrogen (BUN)	Birth/0 to 27 days old (Neonates)	$\geq 4.3 \text{ mmol/L}$ or 12 mg/dL	$CF = g \times 16.66 = \text{mmol}$ Based on normal ranges: 3 to 12 mg/dL (NN; 5 to 18 mg/dL (other classes of age))
	28 days/1 month to 16/18 years old (Infants, Children, Adolescents)	$\geq 6.4 \text{ mmol/L}$ or 18 mg/dL	
Chloride	All age ranges	$\leq 80 \text{ mmol/L}$ or 80 mEq/L $\geq 115 \text{ mmol/L}$ or 115 mEq/L	$CF = 1$ Based on normal range: 98 to 106
Sodium	All age ranges	$\leq 129 \text{ mmol/L}$ or 129 mEq/L $\geq 150 \text{ mmol/L}$ or 150 mEq/L	$CF = 1$ Based on normal range : 134 to 146
Potassium	Birth/0 to 27 days old (Neonates)	$\leq 3.0 \text{ mmol/L}$ or 3.0 mEq/L $\geq 7.0 \text{ mmol/L}$ or 7.0 mEq/L	$CF = 1$ Based on normal ranges: 3.0 to 7.0 (NN); 3.5 to 6.0 (Infants); 3.5 to 5.0 (>Infants)
	28 days/1 month to 23 months old (Infants)	$\leq 3.5 \text{ mmol/L}$ or 3.5 mEq/L $\geq 6.0 \text{ mmol/L}$ or 6.0 mEq/L	
	24 months/2 years to 16/18 years old (Children, Adolescents)	$\leq 3.5 \text{ mmol/L}$ or 3.5 mEq/L $\geq 5.5 \text{ mmol/L}$ or 5.5 mEq/L	
Bicarbonate	All age ranges	$\leq 16 \text{ mmol/L}$ or 16 mEq/L $\geq 30 \text{ mmol/L}$ or 30 mEq/L	$CF = 1$ Based on normal range: 18 to 26

CRITERIA for POTENTIALLY CLINICALLY SIGNIFICANT ABNORMALITIES For Studies in Children			
Parameter	Age range	PCSA	Comments
Calcium total	All age ranges	$\leq 2.0 \text{ mmol/L or } 8.0 \text{ mg/dL}$ $\geq 2.9 \text{ mmol/L or } 11.6 \text{ mg/dL}$	$CF = mg \times 0.025 = \text{mmol}$ Based on normal range: 8.4 to 10.9 mg/dL
Calcium ionized	All age ranges	$\leq 1.0 \text{ mmol/L or } 4.0 \text{ mg/dL}$ $\geq 1.4 \text{ mmol/L or } 5.6 \text{ mg/dL}$	$CF = mg \times 0.025 = \text{mmol}$ Based on normal range: 4.0 to 5.1 mg/dL
Total Cholesterol	All age ranges	$\geq 6.20 \text{ mmol/L or } 240 \text{ mg/dL}$	$CF = g \times 2.58 = \text{mmol}$ Based on normal ranges: 45 to 182 mg/dL (1-3 years), 109 to 189 mg/dL (4-6 years), 126 to 191 mg/dL (Boys 6-9 years), 122 to 209 mg/dL (Girls 6-9 years), 130 to 204 mg/dL (Boys 10-14 years), 124-217 mg/dL (Girls 10-14 years), 114 to 198 mg/dL (Boys 15-19 years), 125 to 212 mg/dL (Girls 14-19 years)
Triglycerides	All age ranges	$\geq 4.0 \text{ mmol/L or } 350 \text{ mg/dL}$	After >12 hours of fast $CF = g \times 1.14 = \text{mmol}$ Based on normal ranges: 30 to 86 mg/dL (Boys 0-5 years), 32 to 99 mg/dL (Girls 0-5 years), 31-108 mg/dL (Boys 6-11 years), 35 to 114 mg/dL (Girls 6-11 years), 36 to 138 mg/dL (Boys 12-15 years), 43 to 138 mg/dL (Girls 12-15 years), 40 to 163 mg/dL (Boys 16-19 years), 40-128 mg/dL (Girls 16-19 years)
Lipasemia	All age ranges	$\geq 2 \text{ ULN}$	Based on normal ranges: 3 to 32 U/L (1-18 years)
Amylasemia	All age ranges	$\geq 2 \text{ ULN}$	Based on normal ranges: 10 to 30 U/L (NN), 10 to 45 U/L (1-18 years)
Glucose	All age ranges	Hypoglycaemia $< 2.7 \text{ mmol/L or } 50 \text{ mg/dL}$ Hyperglycaemia $\geq 7 \text{ mmol/L or } 120 \text{ mg/dL}$ (fasted after >12 hours of fast); $\geq 10.0 \text{ mmol/L or } 180 \text{ mg/dL}$ (unfasted)	$CF = g \times 5.55 = \text{mmol}$ Based on normal ranges: 50 to 90 mg/dL (NN), 60 to 100 mg/dL (Child)
CRP	All age ranges	$> 2 \text{ ULN or } > 10 \text{ mg/L}$ (if ULN not provided)	Based on normal ranges: <6 mg/L
Hematology			
Common Terminology Criteria for Adverse Events v3.0 (CTCAE), 2006; Division of Microbiology and Infections Diseases Pediatric Toxicity Tables, 2007 ; Division of AIDS Table for Grading the Severity of Adult and Pediatric Adverse Events, 2004; Mulberg AE et al. Pediatric Drug Development Concepts and applications. John Wiley & sons, Inc. 2009; Family Practice Notebook, LLC, 2012; Tietz NW et al. Clinical Guide to Laboratory Testing, 3 rd edition 1995			

CRITERIA for POTENTIALLY CLINICALLY SIGNIFICANT ABNORMALITIES For Studies in Children			
Parameter	Age range	PCSA	Comments
WBC	Birth/0 to 27 days old (Neonates)	<4.0 GIGA/L or 4,000 /mm3 >25.0 GIGA/L or 25,000 /mm3	To be used if no differential count available
	28 days/1 month to 23 months old (Infants)	<4.0 GIGA/L or 4,000 /mm3 >20.0 GIGA/L or 20,000 /mm3	Based on normal ranges: 9,000 to 30,000 /mm3 (birth), 9,400 to 38,000 /mm3 (0-1 day), 5,000 to 21,000 /mm3 (1 day-1 month), 6,000 to 17,500 /mm3 (1 month-2 years), 5,000 to 17,000 /mm3 (2-6 years), 4,500 to 15,500 /mm3 (6-11 years), 4,500 to 13,500 /mm3 (11-18 years)
	24 months/2 years to <6 years old (Children)	<3.0 GIGA/L or 3,000 /mm3 >16.0 GIGA/L or 16,000 /mm3	
	6 to <12 years old (Children)	<5.0 GIGA/L or 5,000 /mm3 >17.0 GIGA/L or 17,000 /mm3	
	12 to 16/18 years old (Adolescents)	<4.5 GIGA/L or 5,000 /mm3 >13.5 GIGA/L or 17,000 /mm3	
Lymphocytes (ALC)	Birth/0 to 27 days old (Neonates)	<1.2 GIGA/L or 1,200 /mm3 >17.0 GIGA/L or 17,000 /mm3	Based on normal ranges: 2,000 to 11,500 /mm3 (0-1 days), 2,000 to 17,000 /mm3
	28 days/1 month to 23 months old (Infants)	<2.0 GIGA/L or 2,000 /mm3 >13.5 GIGA/L or 13,500 /mm3	/mm3 (1 month-2 years), 3,000 to 13,500 (2 days-1 month), 1,500 to 9,500 /mm3 (2-6 years), 1,500 to 8,000 /mm3 (6-10 years), 1,200 to 5,200 /mm3 (10-18 years)
	24 months/2 years to <6 years old (Children)	<1.0 GIGA/L or 1,000 /mm3 >9.5 GIGA/L or 9,500 /mm3	
	6 to <12 years old (Children)	<1.0 GIGA/L or 1,000 /mm3 >8.0 GIGA/L or 8,000 /mm3	
	12 to 16/18 years old (Adolescents)	<0.6 GIGA/L or 600 /mm3 >6.0 GIGA/L or 6,000 /mm3	
Absolute Neutrophil Count (ANC)	Birth/0 to 27 days old (Neonates)	<4.0 GIGA/L or 4,000 /mm3 (1 day old) <1.5 GIGA/L or 1,500 /mm3 (2-7 days old) <1.25 GIGA/L or 1,250 /mm3 (>7 day-1 month old) >1 ULN	Based on normal ranges: 5,000 to 28,000 /mm3 (0-1 day), 1,000 to 10,000 (1 day-1 month), 1,000 to 8,500 (1-12 months), 1,500 to 8,500 (1 to 6 years), 1,500 to 8,000 (6 to 10 years), 1,800 to 8,000 (10 to 18 years)
	28 days/1 month to 23 months old (Infants)	<1.0 GIGA/L or 1,000/mm3 (1-3 months) <1.2 GIGA/L or 1,200 /mm3 (3-24 months) >1 ULN	
	24 months/2 years to <6 years old (Children)	<1.2 GIGA/L or 1,200 /mm3 >1 ULN	
	6 to <12 years old (Children)	<1.2 GIGA/L or 1,200 /mm3 >1 ULN	
	12 to 16/18 years old (Adolescents)	<1.2 GIGA/L or 1,200 /mm3 >1 ULN	
Eosinophils	All age ranges	>0.5 GIGA/L or 500 /mm3 Or >ULN if ULN >0.5 GIGA/L or 500 /mm3	Based on normal ranges: 0 to 500 /mm3 (0-1 month), 0 to 300 /mm3 (1 month-18 years)
Hemoglobin	Birth/0 to 27 days old (Neonates)	<86 mmol/L or 12.0 g/dL or any decrease ≥0.31 mmol/L or 2 g/dL	CF = g × 1.55 = mmol Based on normal ranges: 15 to 20 g/dL
	28 days/1 month to 23 months old (Infants)	<1.40 mmol/L or 9.0 g/dL or any decrease ≥0.31 mmol/L or 2 g/dL	(0-3 days), 12.5 to 18.5 g/dL (1-2 weeks), 10.0 to 13.0 g/dL
	24 months/2 years to <16/18 years old (Children, Adolescents)	<1.55 mmol/L or 10.0 g/dL or any decrease ≥0.31 mmol/L or 2 g/dL	(1-6 months), 10.5 to 13.0 g/dL (7 months-2 years), 11.5 to 13.0 g/dL (2-5 years), 11.5 to 14.5 (5-8 years), 12.0 to 15.2 g/dL (13-18 years)

CRITERIA for POTENTIALLY CLINICALLY SIGNIFICANT ABNORMALITIES For Studies in Children			
Parameter	Age range	PCSA	Comments
Hematocrit	Birth/0 to 27 days old (Neonates)	<0.39 l/l or 40% >0.61 l/l or 47%	CF = % × 0.01 = l/l Based on normal ranges: 45 to 61%
	28 days/1 month to 23 months old (Infants)	<0.29 l/l or 29% >0.42 l/l or 42%	(0-3 days), 39 to 57% (1-2 weeks), 29 to 42% (1-6 months), 33 to 38% (7 months-2 years), 34 to 39% (2-5 years), 35 to 42%
	24 months/2 years to <16/18 years old (Adolescents)	<0.32 l/l or 32% >0.47 l/l or 47%	(5-8 years); 36 to 47% (13-18 years)
Platelets	All age ranges	<100 GIGA/L or 100,000 /mm ³ >700 GIGA/L or 700,000 /mm ³	Based on normal ranges: 250,000 to 450,000 /mm ³ (NN); 300,000 to 700,000 /mm ³ (1-6 months), 250,000 to 600,00 /mm ³ (7 months-2 years), 250,000 to 550,000 /mm ³ (2-12 years), 150,000 to 450,000 /mm ³ ((13-18 years))
Urinalysis			Patel HP, Pediatr Clin N Am, 2006
Ketonuria	All age ranges	Presence	Semi-quantitative methods
Glycosuria	All age ranges	Presence	Semi-quantitative methods
Hematuria	All age ranges	≥1+	Semi-quantitative methods
Proteinuria	All age ranges	≥1+	Semi-quantitative methods

5.6 APPENDIX 6 Day ranges for calculating ISS7 and HSS7 weekly scores

Table 13 - Day ranges for calculating ISS7 and HSS7 weekly scores

Analysis visit	Day range for calculating weekly score	Target day
Week 1	2-8	8
Week 2	9-15	15
Week 3	16-22	22
Week 4	23-29	29
Week 5	30-36	36
Week 6	37-43	43
Week 7	44-50	50
Week 8	51-57	57
Week 9	58-64	64
Week 10	65-71	71
Week 11	72-78	78
Week 12	79-85	85
Week 13	86-92	92
Week 14	93-99	99
Week 15	100-106	106
Week 16	107-113	113
Week 17	114-120	120
Week 18	121-127	127
Week 19	128-134	134
Week 20	135-141	141
Week 21	142-148	148
Week 22	149-155	155
Week 23	156-162	162
Week 24	163-169	169
Week 25	170-176	176
Week 26	177-183	183
Week 27	184-190	190
Week 28	191-197	197
Week 29	198-204	204
Week 30	205-211	211
Week 31	212-218	218
Week 32	219-225	225
Week 33	226-232	232
Week 34	233-239	239
Week 35	240-246	246
Week 36	247-253	253

5.7 APPENDIX 7 SELECTION CRITERIA FOR AE GROUPINGS

Table 14 - List of PTs for CMQs

Grouping	Preferred Term/ Medication Code	Preferred Term/ Medication
Conjunctivitis	10001257	Adenoviral conjunctivitis
Conjunctivitis	10010725	Conjunctival irritation
Conjunctivitis	10010726	Conjunctival oedema
Conjunctivitis	10010736	Conjunctival ulcer
Conjunctivitis	10010741	Conjunctivitis
Conjunctivitis	10010744	Conjunctivitis allergic
Conjunctivitis	10010745	Conjunctivitis chlamydial
Conjunctivitis	10010749	Conjunctivitis gonococcal neonatal
Conjunctivitis	10010754	Conjunctivitis tuberculous
Conjunctivitis	10010755	Conjunctivitis viral
Conjunctivitis	10018258	Giant papillary conjunctivitis
Conjunctivitis	10021629	Inclusion conjunctivitis
Conjunctivitis	10030861	Ophthalmia neonatorum
Conjunctivitis	10048908	Seasonal allergy
Conjunctivitis	10049458	Herpes simplex virus conjunctivitis neonatal

Signature Page for VV-CLIN-0685310 v1.0

pkm16982-16-1-9-sap

Approve & eSign

Clinical

Approve & eSign

Clinical

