Any severe type of conjunctivitis	CMQ10498 based on PTs (See Section 5.7 ^a) and "Severe" ticked in Adverse Events eCRF page.
Any severe type of blepharitis	CMQ10497 based on HLT as "Lid, lash and lacrimal infections, irritations and inflammations" and "Severe" ticked in Adverse Events eCRF page.
Keratitis	CMQ10642 based on the following PTs [keratitis, allergic keratitis, ulcerative keratitis, atopic keratoconjunctivitis, herpes ophthalmic, ophthalmic herpes simplex, corneal infection] ^a .
Clinically symptomatic eosinophilia (or eosinophilia associated with clinical symptoms)	CMQ10641 (based on HLT = Eosinophilic disorders or PT = Eosinophil count increased) and AESI is "Yes".
Pregnancy of a female patients entered in a study as well as pregnancy occurring in a female partner of a male patient entered in a study with IMP/NIMP	"Pregnancy" or "Partner Pregnancy" checked on the Pregnancy eCRF page as reported by the investigator.
Significant ALT elevation	ALT >5 × ULN in participants with baseline ALT ≤2 × ULN; OR ALT >8 × ULN if baseline ALT >2 × ULN.
Symptomatic overdose with IMP	Symptomatic Overdose is answered Yes, with Overdose of IMP answered Yes on AE eCRF.
Symptomatic overdose with NIMP	Symptomatic Overdose is answered Yes, with Overdose of NIMP answered Yes on AE eCRF.
Other selected AE Grouping	
Serious injection site reactions or severe injection site reactions that last longer than 24 hours	HLT = 'Injection site reactions' and either with serious status, or with severe status and (AE end date/time - AE start date/time) ≥24 hours or ongoing.
Severe or serious infection	Primary SOC = 'Infections and infestations' and with severe or serious status.
Drug-related hepatic disorder	SMQ [20000006] Drug-related hepatic disorders- narrow.
Injection site reaction	HLT = 'Injection site reactions'.
Malignancy	SMQ [20000091]- Malignant or unspecified tumors narrow.
Conjunctivitis (narrow)	CMQ10644 based on the following PTs [Conjunctivitis, Conjunctivitis allergic, Conjunctivitis bacterial, Conjunctivitis viral, Atopic keratoconjunctivitis] ^a .

AE Grouping	Criteria
Conjunctivitis (broad)	CMQ10645 based on the following PTs [Conjunctivitis, Conjunctivitis allergic, Conjunctivitis bacterial, Conjunctivitis viral, Atopic keratoconjunctivitis, Blepharitis, Dry eye, Eye irritation, Eye pruritus, Lacrimation increased, Eye discharge, Foreign body sensation in eyes, Photophobia, Xerophthalmia, Ocular hyperaemia, Conjunctival hyperaemia] ^a .

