Conjunctivitis (FDA)	CMQ10643 based on the following PTs [Conjunctivitis, Conjunctivitis allergic, Conjunctivitis bacterial, Conjunctivitis viral, Eye irritation, Eye inflammation, Giant papillary conjunctivitis] ^a .
Keratitis (FDA)	CMQ30102 based on the following PTs [keratitis, allergic keratitis, ulcerative keratitis, atopic keratoconjunctivitis, ophthalmic herpes simplex] ^a .

^a The list of terms may be adjusted according to MedDRA version changes

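### The severe-conjunctivitis AESI rule in the SAP counts any seasonal allergy graded Severe, with no check that the eye was involved

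*SAP*

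**What the plan says.** Protocol Section 8.3.7 lists severe conjunctivitis or blepharitis, of any type, among the AESIs. That is an eye event.

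SAP Section 3.5.2, Table 8, turns this into a programmable rule. The severe-conjunctivitis row is "CMQ10498 based on PTs", with the terms given in Section 5.7, and it adds one condition: Severe must be "ticked in Adverse Events eCRF page". Nothing else is required.

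SAP Section 5.7, Table 14, prints 15 PTs under the grouping Conjunctivitis. One complete row, with its own code (10048908), is "Seasonal allergy".

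Footnote a to Table 8 is attached to the cross-reference in this row. It reads "The list of terms may be adjusted according to MedDRA version changes".

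SAP Section 3.5.2 also says that the number and percentage of participants with at least one event will be given for each event of interest in Table 8. Table 7 separately presents all TEAEs and treatment-emergent AESIs by primary SOC and PT.

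**The concern.** A grouped AESI count should contain the events that the protocol defines as that AESI. Here the rule is mechanical: a listed term plus a Severe grade. A child with a severe seasonal allergy confined to the nose or chest would satisfy it and be counted as a case of severe conjunctivitis.

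The topic is not incidental. Protocol Section 2.3.1 lists conjunctivitis among the adverse drug reactions identified for dupilumab, so readers of the safety results will look for this line. In a study this small, one wrongly assigned child visibly changes the reported percentage.

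**Working it through.** The plan states no figure to reproduce. The check compares the lists and criteria, then works out the size of one event.

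**Step 1: the terms in Table 14.** Of the 15 printed PTs:
- 13 contain the word conjunctivitis or conjunctival (for example Adenoviral conjunctivitis, Conjunctival ulcer, Giant papillary conjunctivitis);
- 1 names an eye condition in other words (Ophthalmia neonatorum);
- 1 names neither: Seasonal allergy.

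13 + 1 + 1 = 15. Removing Seasonal allergy leaves 14 terms, each naming a conjunctival or eye condition.

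**Step 2: is there a later filter?** The rows of Table 8 compare as follows.

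| AESI row | Condition beyond the term list |
|---|---|
| Anaphylactic reaction (algorithm-identified cases) | Medical review |
| Systemic hypersensitivity | Corrective treatment, or drug withdrawn or interrupted; then medical review |
| Clinically symptomatic eosinophilia | AESI flag is Yes |
| Severe conjunctivitis | Severe grade only |

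The plan already uses medical review and the AESI flag where a term list alone is not specific. The severe-conjunctivitis row uses neither, so nothing stops a severe seasonal allergy from being counted.

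**Step 3: where the event would appear.** It would add one participant to the severe-conjunctivitis line and could add one to the overview line for any treatment-emergent AESI. In the Table 7 outputs by SOC and PT it would be shown under its own PT.

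**Step 4: size of one event.** SAP Section 4 says enrollment stopped after 15 participants. Assuming all 15 were dosed and so belong to the safety population:

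1 / 15 = 6.7%.

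SAP Section 3.1 also calls for results by intervention group. SAP Section 4 refers to concentration data from at least 7 participants in each of the two weight groups. With 15 in total, the group of 30 kg and above, which is a single regimen (200 mg Q2W), has 7 or 8 children. One event there is 1/8 = 12.5% to 1/7 = 14.3%. Children below 30 kg are spread over three regimens, whose sizes the documents do not give.

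**Step 5: what has to happen first.** The event must be treatment-emergent, coded to Seasonal allergy, graded Severe and without conjunctival involvement. Protocol Section 10.3.3 describes Severe as medically significant, indicating hospitalization, or disabling and limiting self-care. The documents give no rate for such an event, so no expected count can be calculated.

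**The case against.** **The term may be there on purpose.** The documents do not explain how CMQ10498 was built. Seasonal allergy can include eye symptoms, and a sensitive query errs toward over-counting a safety event. This stands as a possible explanation, and calling the term non-ocular rests on its name. But the rule requires no eye involvement, so it can still count an event that is not the AESI defined in the protocol.

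**The event is not hidden.** This stands. Because the SOC and PT tables show it under its own name, a careful reader could trace it. The error is confined to grouped counts.

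**The effect is small.** This stands too. It needs a Severe grade, and SAP Section 3.5 describes the safety analysis as essentially descriptive with no testing, so no decision rule depends on the count.

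**A stronger reading that the documents do not support.** A reader might infer that the term is wrong because the SAP's narrow, broad and FDA conjunctivitis groupings all leave it out. The broad grouping even reaches to "Blepharitis, Dry eye, Eye irritation, Eye pruritus, Lacrimation increased, Eye discharge, Foreign body sensation in eyes, Photophobia, Xerophthalmia, Ocular hyperaemia, Conjunctival hyperaemia". That comparison does not discriminate. Only 4 of the 15 Table 14 terms (Conjunctivitis, Conjunctivitis allergic, Conjunctivitis viral, Giant papillary conjunctivitis) are in any of the three lists. The other 11 are in none, and 10 of those name an eye condition. A severe adenoviral conjunctivitis would likewise be an AESI and be missing from all three. The mismatch comes from using separate queries, and deleting one row would not remove it. Nor is there a case for forcing Table 14 to match: the FDA list, for example, would bring in Eye irritation and Eye inflammation, which are themselves not specific to conjunctivitis.

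**Conclusion.** The point holds, as a minor one. As written, the rule can put a severe seasonal allergy without eye involvement into the severe-conjunctivitis count, contrary to protocol Section 8.3.7. One such child is 6.7% of 15 overall.

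This rests on three things: Seasonal allergy is the only Table 14 term that names no eye condition; the row has no eye-symptom requirement, review step or AESI flag; and all 15 enrolled children were dosed. It does not depend on Table 14 being complete as printed, since only the presence of that one row matters.

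A reader might also infer that footnote a already permits dropping the term. It does not: it covers changes that follow from the MedDRA version, and removing a term on clinical grounds is not one.

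**What to change.** Make a documented SAP change before database lock, in one of two forms:

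1. Remove Seasonal allergy from the study-level PT list for the severe-conjunctivitis AESI; or
2. Keep it, and count it only when the verbatim term or the investigator's AESI flag confirms conjunctival involvement. The eosinophilia row shows that an AESI flag is collected. If that flag does not record which AESI is meant, the verbatim term has to decide.

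The cost is one row of Table 14 or one added criterion in Table 8. No new data are needed. The downside is that the study list, or the way it is applied, would differ slightly from the sponsor's CMQ10498, and this should be footnoted so that pooled summaries can be reconciled.
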